### **9.6.3 Other Safety Measures**

#### **9.6.3.1 *Electrocardiogram Findings***

Shifts from baseline to post-baseline visits for each study part by dose group will be presented for normal, abnormal not clinically significant and abnormal clinically significant ECG findings, as determined by investigator interpretation, for the safety analysis set. Baseline for ECG findings is defined in Section 3.

Electrocardiogram findings will be presented in a data listing for subjects in the safety analysis set.

#### **9.6.3.2 *Spirometry***

Baseline and all post-baseline visit values and change (absolute and relative) from baseline to post-baseline values for FEV1, percent predicted FEV1, FVC, percent predicted FVC, FEV1/FVC, FEF25-75%, and PEF will be summarized for the safety analysis set using

descriptive statistics, as described in Section 3. Baseline for all spirometry parameters is defined in Section 3.

Percent predicted FEV1 results for each subject at each visit by study part and dose group will be provided in line plots for all visits and separately for visits up to Day 29, Day 57, and Day 32 for Part A, Part B, and Part D, respectively. These plots will be provided by dose group (4 mg [Part D only], 8 mg, 12 mg [Part B only], 16 mg, 20 mg, 24 mg [Part A only], and pooled placebo). Additionally, the mean values with standard error for each of the 4 mg dose group (Part D only), 8 mg dose group, 12 mg dose group (Part B only), 16 mg dose group, 20 mg dose group, 24 mg dose group (Part A only), and pooled placebo group will be provided in a line plot for percent predicted FEV1 results for all visits and separately for visits up to Day 29, Day 57, and Day 32 for Part A, Part B, and Part D, respectively. The mean change (absolute and relative) from baseline values with standard error for each of the 4 mg dose group (Part D only), 8 mg dose group, 12 mg dose group (Part B only), 16 mg dose group, 20 mg dose group, 24 mg dose group (Part A only), and pooled placebo group will be provided in a line plot for percent predicted FEV1 results for all post-baseline visits. These line plots will be provided separately for visits up to Day 29, Day 57, and Day 32 for Part A, Part B, and Part D, respectively. Time will be represented proportionally on the x-axis for the Part A and D FEV1 figures.

Spirometry results will be presented in a data listing for subjects in the safety analysis set.

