- Patients with one or more unclassified mutations will be evaluated on a case-by-case basis to determine whether the mutation(s) confers partial CFTR function in the opinion of the Investigator and Sponsor. The Parts B and D Coordinating Investigator will adjudicate eligibility of unclassified mutations as needed.

Patients who are receiving treatment with lumacaftor/ivacaftor or tezacaftor/ivacaftor combination drugs (ORKAMBI or SYMDEKO) will not be excluded from the study. It was felt that these therapies would not significantly interfere with the evaluation of the secondary endpoint based on their modest effect on CFTR protein levels and function, as determined in vitro and in vivo.^{25,26} Patients who are receiving treatment with ivacaftor monotherapy

(KALYDECO) will be excluded because KALYDECO is not approved for use in patients with Class I or Class II mutations. For Parts A and B only, elexacaftor/tezacaftor/ivacaftor triple combination therapy (TRIKAFTA) will be excluded because of the potential of this therapy to confound the evaluation of the secondary endpoint. Subjects in Parts A and B who are eligible for TRIKAFTA may switch/start on TRIKAFTA; however, subjects must not start/switch until at least 2 months after their last dose of study drug so as not to confound the interpretation of the primary and secondary endpoints. Patients who are receiving treatment with TRIKAFTA will not be excluded from Part D of the study.

Women of childbearing potential may participate in the study based on the rationale that CF disease is serious and affects women. The study design includes measures to minimize the possibility of fetal exposure to the IP. This consists of pregnancy testing prior to participation in the study and the use of an acceptable form of contraception if the subject is sexually active during the course of the study (Section 4.4.1). Females of childbearing potential currently taking the lumacaftor/ivacaftor combination drug (ORKAMBI) and using oral hormonal contraceptives will be required to take an additional or alternative method of contraception to prevent pregnancy in this study. The informed consent provides female subjects with sufficient information so that they may make informed decisions about the potential risks and benefits of the therapy and the study.

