5.1.2. Prohibited Medications

Specific medications not permitted during the study are listed below:

- Ivacaftor monotherapy (KALYDECO)
- Parts A and B only: Triple-combination therapy (TRIKAFTA)

Starting on or switching to TRIKAFTA is acceptable during the follow-up period; however, subjects should not start/switch until at least 2 months after their last dose of study drug so as not to confound the interpretation of the primary and secondary endpoints.

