## **11. OTHER ANALYSES**

### **11.1 Cystic Fibrosis Questionnaire-Revised (CFQ-R)**

For Part B, the CFQ-R respiratory domain scores at baseline (Day -1) and Days 36, 43, 57, 85, 113, 197, 281, and 365 will be summarized for the safety analysis set by dose group using descriptive statistics, as described in Section 3. Change from baseline to post-baseline in CFQ-R respiratory domain scores will be calculated for each subject with data at baseline and the post-baseline visit. The mean change from baseline will be summarized for the safety analysis set by dose group at Days 36, 43, 57, 85, 113, 281, and 365.

CFQ-R respiratory domain scores at each visit will be presented in a data listing for Part B subjects in the safety analysis set.

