**Notes:**

- 1) *Parameters include: FEV1, Percent Predicted FEV1, FVC, Percent Predicted FVC, FEV1/FVC, FEF25-75%, PEF*
- 2) *Include all planned (per the protocol) post-baseline visits/timepoints where spirometry is performed and collected.*

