**Notes:**

- 1) **Include Baseline (Day -1) and Days 36, 43, 57, 85, 113, 281, and 365.**

Footnotes

Data Type	Footnote Type	Code	Prefix	Footnote
All	Percent	PC_F02	Note:	Percentages were based on the number of subjects (N) in the population analyzed.
All	Baseline	BL_F01	Note:	Baseline was defined as the last measurement taken prior to the first dose, obtained on or prior to the day of first dose of study drug.
All	Baseline	BL_F01P	Note:	Baseline was defined as the Screening measurement.
All	Baseline	BL_F01S	Note:	Baseline was defined as the Day -1 complete physical exam.
All	Change from Baseline	CH_F01	Note:	Change from baseline was defined as visit value - baseline value.
All	Change from Baseline	CH_F02	Note:	Relative change from baseline was defined as (visit value - baseline value)/(baseline value)*100.
All	By Visit	VIS_F01		n = Number of subjects with the specified result at the specified visit and non-missing baseline result; nn = Number of subjects with a non-missing result at the specified visit; (%) = Percentage of subjects with the specified result at the specified visit.
All	By Visit	VIS_F01a		n = Number of subjects with the specified result at the specified visit; nn = Number of subjects with a non-missing result at the specified visit; (%) = Percentage of subjects with the specified result at the specified visit.
All	Abbreviation	AB_F01		SD = standard deviation; SE = standard error
All	Abbreviation	AB_F01a		SD = standard deviation
All	Abbreviation	AB_F02		CFTR = cystic fibrosis transmembrane conductance regulator; FEV 1 = forced expiratory volume in 1 second; SD = standard deviation
All	Abbreviation	AB_F03		AE = adverse event; IP = investigational product; TEAE = treatment-emergent adverse event
All	Abbreviation	AB_F04		AE = adverse event; TEAE = treatment-emergent adverse event
All	Abbreviation	AB_F05		CS = clinically significant; ECG = electrocardiogram; NCS = not clinically significant
All	Abbreviation	AB_F06		CFQ-R = Cystic fibrosis questionnaire-revised; SD = standard deviation; SE = standard error
DS	Percent	DS_F03	[2]	The denominator was defined as the total number of subjects who discontinued the study.
DM	Age	DM_F01	[1]	Age was calculated by (date of informed consent - date of birth)/365.25, rounded down to the next largest integer using the floor function, in years.

Data Type	Footnote Type	Code	Prefix	Footnote

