DM	CFTR	DM_F02	[2]	CFTR Modulator use at baseline was defined as a concomitant CFTR modulator that was in use at the start of treatment, or a CFTR modulator with missing start date.
CM	Percent	CM_F01	Note:	n = Number of subjects that reported at least 1 medication within an Anatomic Class, Therapeutic Class, and Medication Term; (%) = Percentage of subjects among the population analyzed (N).
CM	Count	CM_F02	Note:	A subject that reported more than 1 medication for a particular Anatomic Class was counted only once for each Anatomic Class.
CM	Count	CM_F03	Note:	A subject that reported more than 1 medication for a particular Therapeutic Class was counted only once for each Therapeutic Class.
CM	Count	CM_F04	Note:	A subject that reported more than 1 medication for a particular Medication Term was counted only once for each Medication Term.
CM	Order	CM_F05	Note:	Medications were presented in order of decreasing frequency, by Anatomic Class, Therapeutic Class, and Medication Term.
CM	Definition	CM_F06	Note:	Concomitant medications included all medications in use at date of first study drug dose or started after date of first study drug dose, any medications that started prior to the day of first dose of study drug with missing stop date, any medications with missing start and stop dates or were classified as ongoing.
CM	Definition	CM_F07	Note:	Prior medications included all medications that stopped prior to the day of first dose of the study drug, medications that started prior to the day of first dose of study drug with missing stop date or medications with missing start and stop dates.
CM	Dictionary	CM_F08	Note:	Anatomic Class, Therapeutic Class, and Medication Term were based on the WHO Drug Global (2020-SEP) coding dictionary.
MH	Count	MH_F01	Note:	If a subject had more than 1 medical history event within a system organ class, the subject was counted only once in that system organ class. If a subject had more than 1 medical history event that coded to the same preferred term, the subject was counted only once for that preferred term.
AE	Count	AE_F05	[1]	Subjects that experienced 1 or more adverse events were counted once.
AE	Count	AE_F06a	[2]	If a subject experienced more than 1 adverse event, the subject was counted only once for the closest relationship to IP. AEs with missing relationships to IP were classified as being Related to IP.

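### Late spirometry and ppFEV1 displays (Parts A and B), and secondarily the Part B CFQ-R table, do not mark values taken after a permitted TRIKAFTA start

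*SAP*

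**What the plan says.** **Protocol.** Section 2.2.2 says that TRIKAFTA, for Parts A and B, "will be excluded because of the potential of this therapy to confound the evaluation of the secondary endpoint". The same section allows a later start: "Subjects in Parts A and B who are eligible for TRIKAFTA may switch/start on TRIKAFTA". Section 5.1.2 repeats the permission for the follow-up period with a delay: "subjects should not start/switch until at least 2 months after their last dose of study drug so as not to confound the interpretation". It names both endpoints, primary and secondary, as what the delay protects. Spirometry continues to Day 337 in Part A and Day 365 in Part B, and CFQ-R (Part B only) to Day 365.

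**SAP, spirometry.** Section 9.6.3.2 covers "Baseline and all post-baseline visit values and change (absolute and relative) from baseline to post-baseline values". The notes to Table 14.3.9.1 say "Include all planned (per the protocol) post-baseline visits/timepoints where spirometry is performed and collected", and Table 14.3.9.2 repeats that table for relative change. Figures 14.3.9.3, 14.3.9.4 and 14.3.9.4.2 plot group means with standard errors over all visits. Separate versions stop at Day 29 (Part A) and Day 57 (Part B).

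**SAP, CFQ-R.** Section 11.1, under Other Analyses, summarises scores at eight post-baseline visits to Day 365, and mean change "by dose group at Days 36, 43, 57, 85, 113, 281, and 365". The Table 14.4.1 notes give the same visits: "Include Baseline (Day -1) and Days 36, 43, 57, 85, 113, 281, and 365". Day 197 is in the list of scores but not in the list of changes. That is a separate inconsistency, noted here only because it affects the counts below.

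**SAP, modulator use.** The one derived variable is fixed at entry (footnote DM_F02): "CFTR Modulator use at baseline was defined as a concomitant CFTR modulator that was in use at the start of treatment", or one with a missing start date.

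**The concern.** The protocol names a confounder of its secondary endpoint and then permits it during part of the period in which that endpoint is still measured. The 2-month delay protects the earlier values only. From then on, the SAP combines values taken with and without TRIKAFTA in the same by-visit group mean, and neither the mean nor its standard-error bar shows which values are which.

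Groups are very small: 3 active subjects per dose level as randomised, and 4 pooled placebo subjects per part. One person starting an effective modulator could look like a late drift in a dose group, or like a late rise on placebo.

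Late Part B data are also meant to be used. Protocol 9.5 plans an interim analysis of all Part B groups with data to at least Day 197, and says that interim data will inform Phase 2 dose and design. The interim analysis plan is a separate document, so this shows only that late Part B values are not merely archived.

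**Working it through.** The plan states no figure to reproduce: the analysis is descriptive and the sample size has no statistical basis. The check has three parts.

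**1. Earliest permitted start = last-dose day + 2 months.**

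The protocol does not define 2 months in days. Protocol 1.5 equates 12 months with 48 weeks, so 2 months can be 8 weeks = 56 days. Two 31-day calendar months give 62 days.

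- Part A (dose on Day 1): 1 + 56 = Day 57, to 1 + 62 = Day 63.
- Part B (fifth dose on Day 29): 29 + 56 = Day 85, to 29 + 62 = Day 91.

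**2. Which visits can be exposed.**

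*Nominal visit days strictly after the earliest start:*

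- Part A follow-up clinic visits are Days 3, 8, 15, 29, 57, 85, 169, 253 and 337. Exposed: 85, 169, 253, 337, so 4 of 9.
- Part B follow-up clinic visits are Days 36, 43, 57, 71, 85, 113, 197, 281 and 365. Exposed: 113, 197, 281, 365, so 4 of 9.
- CFQ-R scores: Days 113, 197, 281 and 365, so 4 of 8. CFQ-R mean changes: Days 113, 281 and 365, so 3 of 7.

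*56-day reading, counting a start on or just before the visit:* Part A Day 57 and Part B Day 85 are added. This is possible because both visits carry ±3-day windows, which Protocol 7.1 and 7.2 call suggestions, and because Part B doses may fall ±1 day. A fifth dose on Day 28 gives 28 + 56 = Day 84. The counts become 5 of 9, 5 of 9, 5 of 8 and 4 of 7.

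*Against all planned post-baseline spirometry timepoints:*

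- Part A adds Day 1 at 8 hours and Day 2, so 9 + 2 = 11. Exposed: 4 to 5 of 11.
- Part B adds Day 1 at 6 hours (1), pre-dose and 6 hours on Days 8, 15, 22 and 29 (8), and Days 2, 9, 16, 23 and 30 (5), so 9 + 14 = 23. Exposed: 4 to 5 of 23.

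A Part B subject who stops after the first dose reaches the limit at Day 57 to 63. Protocol 2.2.3 reports one such subject, and Protocol 4.5.1 asks that discontinued subjects still be followed. For such a subject, Days 71 and 85 (spirometry) and Day 85 (CFQ-R) are also exposed.

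**3. How far one starter moves a mean: shift = individual change / n.**

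The documents give no TRIKAFTA effect. Individual ppFEV1 changes of 5, 10 and 15 points are assumed.

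| Individual change | n = 3 (active arm) | n = 4 (pooled placebo, 4 groups × 1) |
|---|---|---|
| 5 | 1.67 | 1.25 |
| 10 | 3.33 | 2.50 |
| 15 | 5.00 | 3.75 |

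An active arm also reaches n = 4 if a subject is replaced, because the safety set keeps everyone dosed.

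The standard-error bar moves too. If one of three subjects changes by d and the others by 0, the SD is d/√3 and the SE is d/3, or 1.67 to 5.00 over the same range.

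For CFQ-R, Protocol 7.5.4 gives 4 points as the minimal clinically important change from baseline. Used only for scale, a group mean moves by 4 if one of 3 subjects rises by 4 × 3 = 12, or one of 4 by 4 × 4 = 16.

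**The case against.** **The protocol already handles this.** The delay is a deliberate design choice, and the ppFEV1 figures cut at Day 29 and Day 57 match it. This stands for the early displays: the cut figures and early table rows precede any permitted start for subjects who took all doses. It does nothing for the late rows and all-visit figures, and CFQ-R has no cut version.

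**A start can be traced.** A reader might infer that the outputs give no way to connect a TRIKAFTA start with the affected values. The documents do not support that. Listing 16.2.14.1 gives medication start dates with study day, and Listings 16.2.13.1 and 16.2.15.1 carry subject number and study day, so the three can be matched by hand. Tables print each subject's value, the individual ppFEV1 plots (Figure 14.3.9.1.2) carry subject IDs, and the concomitant-medication table shows whether a dose group has any user. What remains is that no display makes the match. The shell rows read only Subject 1 to 4, the medication table has no dates, and a mean with an error bar cannot show the start.

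**Nobody may have started.** Inclusion criterion 7 and Protocol 5.1.1 expect stable CF medication, and only eligible subjects may switch. The coverage of about 90% in Protocol 1.3.2 describes mutations across CF patients; it is not uptake in this Class I/II population. All of this stands and limits the weight.

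**CFQ-R is peripheral, and other treatments are unflagged too.** CFQ-R is not a primary or secondary endpoint, and the protocol's confounding statements do not name it, so it is secondary here. Antibiotics, corticosteroids and extra bronchodilators for exacerbations are also permitted without a flag. TRIKAFTA differs because the protocol itself names it as a confounder, but removing post-TRIKAFTA values would not free the late visits of every influence.

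**Conclusion.** The point holds for the late displays in Parts A and B. Followed as written, the SAP can produce late group means on 3 or 4 subjects that mix in, unmarked, a treatment the protocol calls a confounder. Exposed follow-up spirometry visits number 4 to 5 of 9 in each part (4 to 5 of 11 and 4 to 5 of 23 planned timepoints). For CFQ-R they are 4 to 5 of 8 scores and 3 to 4 of 7 mean changes. The lower counts rest on nominal days and visits strictly after the earliest start; the upper counts rest on the 56-day reading with same-day or just-earlier starts included. The ppFEV1 shifts of 1.7 to 5.0 (n=3) and 1.25 to 3.75 (n=4) rest on an assumed individual effect of 5 to 15 points and a single starter.

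A reader might go further and infer that the late results are in fact confounded, or that the secondary endpoint is compromised as a whole. The documents support neither. They record no TRIKAFTA start, early displays are protected, no test or planned between-group estimate is affected, and late visits serve mainly as safety follow-up. The consequence is confined to how late group displays are read. The change should be made because it is cheap and uses data already collected. Part D is outside the point, since TRIKAFTA is permitted there at entry.

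**What to change.** Leave the all-data tables and figures as the main displays, because spirometry is also part of the primary safety endpoint. The protocol's rule on when TRIKAFTA may be started is not in question. In SAP 9.6.3.2 (Parts A and B) and 11.1 (Part B):

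1. Derive the date of any post-baseline TRIKAFTA start or switch from the concomitant-medication data.
2. Flag spirometry and CFQ-R values dated on or after it, in the by-visit tables (14.3.9.1, 14.3.9.2, 14.4.1) and in Listings 16.2.13.1 and 16.2.15.1.
3. Mark the date on the individual all-visit ppFEV1 plots (Figure 14.3.9.1.2). The Part B figure to Day 57 already uses a symbol for dosing days.
4. If any subject started, add a supplementary late-visit summary of ppFEV1, and of CFQ-R in Part B, without flagged values. Show n at each visit, and label the summary as descriptive and selected by a post-randomisation event. Read it beside the main display, not in its place.
5. If none started, say so in one line and omit the supplement.

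The cost is SAP wording, one derived date and flag, a plot mark and at most one extra summary per endpoint. No new data are needed. The drawback is that the supplement may rest on 1 or 2 subjects in an arm, with no SD at n=1.

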#### ***9.6.3.3 Chest X-ray***

Shifts from baseline to post-baseline visits for each study part by dose group will be presented for normal, abnormal not clinically significant and abnormal clinically significant assessments for the safety analysis set. Chest x-ray findings will be presented in a data listing for subjects in the safety analysis set.

#### ***9.6.3.4 Prior and Concomitant Medications and Procedures***

The prior and concomitant medications will be coded using the latest version of World Health Organization Drug Dictionary (WHO Drug) Global (2020-SEP) to identify the drug class and preferred drug name.

Concomitant medications will include all medications that started on or after day of first dose of the study drug or that stopped on or after day of first dose of study drug, including medications that are classified as ongoing. Prior medications will include all medications that started and stopped prior to the day of first dose of the study drug. Any medication with a missing stop date (i.e., day, month, and year are missing) will be classified as ongoing. For a medication with a missing start date, the medication will be classified as both a prior and concomitant medication unless the stop date is prior the date of first dose of study drug, in which case the medication will be classified as a prior medication. For medications with start date prior to the date of first dose of study drug and missing end date, the medication will be classified as both prior and concomitant. Medications with missing start and stop dates will be classified as prior and concomitant.

The number and percentage of subjects using prior medications, and separately concomitant medications, will be tabulated by Anatomical Therapeutic Chemical (ATC) level 1 term, ATC level 2 term, and preferred drug name for all subjects in the safety analysis set by study part and dose group, and also for the study overall. If a subject has more than 1 medication within an ATC level 1 term, the subject will be counted only once in that ATC level 1 term. Similarly, if a subject has more than 1 medication within an ATC level 2 term, the subject will be counted only once in that ATC level 2 term. If a subject has more than 1 medication that codes to the same preferred drug name, the subject will be counted only once for that preferred drug name. All percentages will use the number of subjects in the safety analysis set as the denominator. The tabular summaries will be sorted by overall (MRT5005 + Placebo) descending frequency by ATC level 1 term, ATC level 2 term, and preferred drug name.

Prior and concomitant medication data will also be presented in a data listing for subjects in the safety analysis set.

Concomitant surgical procedures will also be presented in a data listing for subjects in the safety analysis set.

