2.4. Study Endpoints

2.4.1. Primary Endpoint

The safety and tolerability of nebulized MRT5005 will be assessed based on the types, frequency, and severity of treatment-emergent AEs including pulmonary exacerbations; concomitant medication use; and changes from baseline in physical examination, weight, vital signs, oxygen saturation (pulse oximetry), ECG, standard clinical laboratory tests, chest x-ray, and spirometry as a measure of pulmonary function.

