5.1.1. Permitted Medications and Therapies

Subjects should remain on a stable medication regimen for CF from at least 28 days prior to the screening visit through the final study visit on Day 337 (± 3 days) in Part A, Day 365 (± 3 days) in Parts B, or Day 341 (± 3 days) in Part D of the study. These may include but are not limited to routine inhaled therapies directed at airway clearance and management of respiratory infections, such as bronchodilators, rhDNase (PULMOZYME), hypertonic saline, antibiotics, and steroids; and other routine CF-related therapies such as systemic antibiotics, pancreatic enzymes, multivitamins, and diabetes and liver medications. The timing of subject participation and routine treatment with cycled inhaled antibiotics will be left up to the discretion of the Investigator.

Hormone replacement therapies, thyroid hormone replacement therapy, and non-steroidal inflammatory drugs are also permitted.

Any other medications which are considered necessary for the subject's safety and well-being may be given at the discretion of the Investigator. For example, for subjects experiencing a pulmonary exacerbation, therapeutic interventions may include oral or intravenous administration of antibiotics, oral or parenteral nutritional support, frequent airway clearance techniques, augmented bronchodilator therapy, and corticosteroids.

Other specific medications permitted during the study are listed below:

- Hormonal contraceptives for females of childbearing potential administered according to the package insert (see Section 4.4.1).
- Lumacaftor/ivacaftor combination drug (ORKAMBI) or tezacaftor/ivacaftor combination drug (SYMDEKO). For Part D only: elexacaftor/tezacaftor/ivacaftor triple combination (TRIKAFTA). To be eligible, subjects must have been on stable treatment with these medications for at least 28 days prior to the screening visit and should remain on it for the duration of the study.

Subjects should remain on their routine CF therapies, which include but are not limited to airway clearance techniques.

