5.1.1.1. Modifications of Subject's Routine Pulmonary Medications and Therapies

If feasible for the subject, all spirometry testing should be performed “pre-bronchodilator” if the subject is receiving treatment with a short-acting beta-agonist or anticholinergic bronchodilator (eg, beta-agonist medication such as albuterol or anticholinergic agent such as ipratropium bromide). These medications should be withheld for at least 4 hours before spirometry testing (Section [7.5.2.12](#)).

On the days of IP dosing, the administration of IP should optimally occur within 2-3 hours after subjects have completed their routine pulmonary therapies (airway clearance and pulmonary medications) for the day. For subjects whose routine airway clearance therapies do not include an inhaled short-acting beta-agonist (or it is not given within the 2 to 3 hour window prior to IP administration), albuterol (2 to 4 puffs) will be administered via metered-dose inhaler approximately 20 minutes before nebulization with IP to minimize any bronchoconstrictive effects. Note that administration of short-acting beta-agonist via nebulization is also permitted at the discretion of the Investigator.

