### **2.2 Study Endpoints**

#### **2.2.1 Primary Endpoint**

The safety and tolerability of nebulized MRT5005 will be assessed based on the types, frequency, and severity of treatment-emergent AEs including pulmonary exacerbations; concomitant medication use; and changes from baseline in physical examination, weight, vital signs, oxygen saturation (pulse oximetry), ECG, standard clinical laboratory tests, chest x-ray, and spirometry as a measure of pulmonary function.

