##### **PROGRAMMER NOTES**

Programmer notes appear at the bottom of each table display shell where applicable.

Dose groups for each part are as follow:

- Part A: MRT5005 8mg, MRT5005 16mg, MRT5005 20mg, MRT5005 24mg, Pooled Placebo
- Part B: MRT5005 8mg, MRT5005 12mg, MRT5005 16mg, MRT5005 20mg, Pooled Placebo
- Part D: MRT5005 4mg, Placebo

For the overall tables, the treatment groups will be Pooled MRT5005 and Pooled Placebo.

Column labels in the mock tables use MRT5005 Xmg and Pooled Placebo. For Part D tables, Placebo should be used and not Pooled Placebo.

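### The only table of concomitant medication use, a primary-endpoint component, merges background drugs and the pre-dose beta-agonist with new treatment, so new treatment in commonly used classes is diluted or hidden

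*SAP*

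**What the plan says.** Protocol 2.4.1 and SAP 2.2.1 both name this component in the primary endpoint; the SAP text reads "severity of treatment-emergent AEs including pulmonary exacerbations; concomitant medication use".

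SAP 9.6.3.4 gives a two-part definition: "Concomitant medications will include all medications that started on or after day of first dose of the study drug" and then "or that stopped on or after day of first dose of study drug, including medications that are classified as ongoing". Footnote CM_F06 in the table specifications repeats it: "Concomitant medications included all medications in use at date of first study drug dose or started after date of first study drug dose". The table counts subjects by ATC level 1, ATC level 2 and preferred drug name, once per row, by study part and dose group and for the study overall. There is no split by start date, time interval, indication or relation to an AE.

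Two protocol provisions determine what fills the table:
- Section 5.1.1: "Subjects should remain on a stable medication regimen for CF from at least 28 days prior to the screening visit", continuing to the final visit.
- Section 5.1.1.1: for subjects who have not taken their own short-acting beta-agonist within the 2 to 3 hours before dosing, "albuterol (2 to 4 puffs) will be administered via metered-dose inhaler approximately 20 minutes before nebulization with IP".

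The drawn shell of Table 14.3.10.1 has three MRT5005 columns and a Total; Table 14.3.10.2 reuses it. The general programmer notes say otherwise: "Column labels in the mock tables use MRT5005 Xmg and Pooled Placebo". SAP Section 3 also requires a pooled placebo column in displays by dose group.

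**The concern.** As a safety measure, medication use is informative when it shows treatment that was needed after dosing: a bronchodilator for bronchospasm, an antipyretic for fever, a new steroid or antibiotic. The protocol anticipates the first two problems. Bronchospasm appears in the stopping criteria and in the definition of the AE of special interest, and Protocol 2.2.3 reports febrile reactions in seven subjects.

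The planned table does not isolate such treatment. A subject already counted in a class row through background therapy cannot be counted again when something new is given. Other unrelated starts also enter during follow-up. For example, Protocol 5.1.2 lets Part A and B subjects begin TRIKAFTA from two months after the last dose, and no time split sets these apart. At stake is whether the tabular summary of a primary-endpoint component can be read as evidence about treatment prompted by MRT5005.

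**Working it through.** The plan states no medication-use rate and no figure to reproduce. The check compares the rules with each other and then illustrates the dilution with assumed rates.

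**1. Who is in the table.** Parts A and B each have four groups of 3 MRT5005 and 1 placebo; Part D has 6 and 2 (SAP 2.3 and 2.5). MRT5005: 12 + 12 + 6 = 30. Placebo: 4 + 4 + 2 = 10. Total: 40.

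**2. What enters.** The SAP definition works at day level. A chronic drug still in use on Day 1 qualifies. So does albuterol given 20 minutes before the first dose, because it falls on the first-dose day. A drug started on any later day up to the final visit (Day 337, 365 or 341 in Parts A, B and D) qualifies too. All three kinds share the same rows.

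**3. The beta-agonist class.** Under Protocol 5.1.1.1 every dosed subject has either taken their own short-acting beta-agonist or received albuterol before dosing. If these are recorded as Protocol 5.1 requires, the ATC level 2 row containing them is at or near 40/40. Suppose 2 of 3 MRT5005 subjects in a Part A dose group needed a bronchodilator after dosing and none of the 4 pooled placebo subjects did. The class row would still read 3/3 and 4/4.

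**4. Other classes.** Let c be the proportion already using a class, taken as equal in both arms, and let r be the new-start rate among non-users. The table shows c + (1 − c)r in each arm, so the visible difference is (1 − c)(r_active − r_placebo). For c = 0.75 with rates of 0.67 and 0.25:
- MRT5005: 0.75 + 0.25 × 0.67 = 0.9175
- placebo: 0.75 + 0.25 × 0.25 = 0.8125
- difference: 0.105

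Visible difference in percentage points for three assumed pairs of rates:

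| c | 67% vs 25% | 50% vs 10% | 100% vs 0% |
|---|---|---|---|
| 0 | 42 | 40 | 100 |
| 0.50 | 21 | 20 | 50 |
| 0.75 | 10.5 | 10 | 25 |
| 0.90 | 4.2 | 4 | 10 |
| 1.00 | 0 | 0 | 0 |

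The first row is also what a summary restricted to new starts would show.

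**5. Whether another medication display separates new starts.** The prior-medication table does not. A background drug that began before Day 1 and has a recorded stop date after it is concomitant only, exactly like a new start. One with a missing stop date is counted as both prior and concomitant. Listing 16.2.14.1 does hold start and stop dates with study day, indication and a 'Taken for AE?' field, but only entry by entry.

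**6. The columns.** The shell omits placebo. SAP Section 3 and the programmer notes require it, the shell's own sorting note ranks rows by MRT5005 plus placebo frequency, and the study-overall version is Pooled MRT5005 against Pooled Placebo by rule.

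**The case against.** The strongest reply is that the table is only one of several displays. Febrile reactions (Tables 14.3.2.4 and 14.3.2.5), pulmonary exacerbations (14.3.2.3) and all treatment-emergent AEs by time interval (14.3.1.2) are tabulated against placebo. New or changed antibiotic therapy is built into the exacerbation definition in Protocol 8.1.7. With three active subjects per dose group in Parts A and B, a colleague can read the listing subject by subject. Protocol 9.8.1 asks only that concomitant medications be summarized, and every analysis is descriptive.

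Much of this stands. It limits the consequence, because the events behind the treatment are visible elsewhere. It does not supply a summary of the treatment itself, and the SAP tabulates its other safety data at the same group sizes.

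A second reply also stands. Rows go down to preferred drug name, so an antipyretic or steroid that nobody was using beforehand would show a difference. No row is dedicated to short-acting beta-agonists, and since subjects may use different agents, no single drug-name row need reach 100%. The saturation is at class level.

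From the drawn shell a reader might infer that the sponsor plans no placebo comparison for this component. The documents do not support that. Section 3, the programmer notes and the sorting rule all include placebo, so the missing column is an inconsistency in one shell.

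**Conclusion.** The point holds for classes in common background use. There the only table of this primary-endpoint component dilutes new treatment by (1 − c). In the ATC level 2 class containing short-acting beta-agonists, post-dose rescue use cannot move the row at all. This rests on pre-dose beta-agonist use being recorded as a medication. The point sizes for other classes rest on assumed rates and on equal background use in both arms, because the documents give neither.

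A reader might go further and conclude that the plan cannot show any treatment prompted by MRT5005, or that a finding of no difference is built in. That is not supported. Drug names without background use remain informative, the listing flags drugs taken for an AE, the underlying events are tabulated against placebo, and the SAP nowhere commits to a between-arm conclusion on medication use. The gap is a worthwhile, inexpensive improvement to a descriptive summary. It does not invalidate the safety analysis.

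**What to change.** Add one descriptive table, by dose group and pooled placebo, with rows by class and preferred name, for the SAP's existing intervals (through Day 29, 57 and 32 in Parts A, B and D, and overall). It should have two blocks:

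- (a) Medications with 'Taken for AE?' equal to Yes. This block captures rescue use of a drug the subject already takes.
- (b) Medications first started after the first dose, excluding the pre-IP beta-agonist on every dosing day. An exclusion limited to Day 1 would not be enough: albuterol given before doses 2 to 5 in Parts B and D, if recorded as separate entries, would otherwise count as new.

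Do not use the SAP 9.1 date imputation to label a drug as new. In the month of first dose it can move an unknown start day to the first-dose date, which would turn a background drug into a new start. Show drugs whose partial start date could precede the first dose in a separate line.

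State a convention for entries starting on a dosing day. The listing shell shows dates without clock times, so it should say how pre-dose and post-dose use are told apart.

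Correct the shells of Tables 14.3.10.1 and 14.3.10.2 to carry the Pooled Placebo column (labelled Placebo in Part D).

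The cost is one extra table, two corrected shells and the date conventions. Start date, indication and the AE flag are already planned for the listing, so no new data collection is foreseen for the core of the table.
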